6. STATISTICAL CONSIDERATIONS AND ANALYSIS PLAN

The intent-to-treat (ITT) population is defined as all randomized patients. Patients in the ITT population will be assigned to treatment groups as randomized.

The safety population is defined as *all patients randomized, taking at least one dose of randomized Sildenafil/Placebo treatment*. Patients in the safety population will be assigned to treatment groups according to the treatment they received.

The primary analysis of the study will be conducted when all patients completed the 52 weeks treatment phase and the mandatory 4 weeks Follow-up visit.

6.1 DETERMINATION OF SAMPLE SIZE

There are no reference data available on the use of pirfenidone in this patient population with a measurable DLCO \leq 40% of predicated value and mPAP \geq 20 mmHg on RHC. A total sample size of approximately 176 patients is planned, and patients will be randomized 1:1 to the two treatment groups. The statistical hypothesis for the treatment comparison is based on the proportion of patients who experienced a \geq 15% decline from baseline in 6MWD, were hospitalized for cardiac- or respiratory non-elective reasons, or who died, according to a pooled analysis of the effects observed in the pirfenidone groups of three large Phase III trials (CAPACITY 1, CAPACITY 2, and ASCEND).

The planned sample size is based on the primary endpoint, proportion of patients with disease progression and assumes 80% power and a one-sided significance level of 5%. Given the disease progression rate of 72% by 52 weeks in the three large registration trials for pirfenidone, and assuming an additive effect of sildenafil on pirfenidone, a disease progression rate of 54% in the combination treatment group is assumed and an absolute difference of 18% (respectively a relative reduction of 25%) in disease progression rates is considered a clinically meaningful treatment benefit.

6.2 SUMMARIES OF CONDUCT OF STUDY

Patient enrollment, duration of follow up, discontinuation from the study, and reasons for discontinuation will be summarized by treatment arm for all randomized patients. In addition, major protocol violations will be summarized by treatment arm.

6.3 SUMMARIES OF DEMOGRAPHIC AND BASELINE CHARACTERISTICS

Demographics and baseline characteristics, such as age, sex, and race, will be summarized by treatment arms using means or medians for continuous variables and proportions for categorical variables. Medical history will be tabulated by treatment arms. Summary of concomitant medications will be displayed by treatment arms in frequency tables.

6.4 EFFICACY ANALYSES

The primary and secondary efficacy analyses will include all randomized patients, with patients grouped according to their assigned treatment.

6.4.1 Primary Efficacy Endpoint

The primary efficacy objective for this study is to evaluate the efficacy of adding sildenafil compared with placebo to pirfenidone treatment in patients with advanced IPF and *risk* of Group 3 PH.

The primary efficacy endpoint will be evaluated based on a comparison of the proportion of patients showing disease progression over 52 weeks of treatment period, as evidenced by reaching the following combined endpoint:

- Relative decline in 6MWD of at least 15% from baseline (as defined below*), respiratory-related non-elective hospitalization, or all-cause mortality

* Relevant decline in 6MWD from baseline is defined as:

- Any decline >25% from baseline or
- A decline between 15-25% from baseline, if accompanied by at least one of the following:
 - worsening of SpO₂ desaturation during the 6MWT compared to baseline

- worsening of the maximum Borg scale during the 6MWT compared to baseline
- increased O₂ requirements during the 6MWT compared to baseline.

The primary analysis will be based on the ITT population, defined as all randomized patients. Patients who discontinue treatment prematurely will be analyzed based on the available data. No imputation method will be applied. Patients who undergo lung transplantation during the study will be withdrawn from the study at the time of hospitalization for transplantation. *In addition, sensitivity analysis of the primary endpoint will be performed. The details of those analyses will be provided in the Statistical Analysis Plan.*

The primary analysis of the primary endpoint will compare disease progression rates in each treatment arm using a Chi-square test with a one-sided significance level $\alpha = 0.05$.

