- Screening period
 - +/- 28-day washout period (if needed); *this can be part of the Run-in period if the Run-in period is applicable*
 - Screening period (up to 28 days). Patients will be evaluated for eligibility based on the inclusion and exclusion criteria
- Double-blind treatment period (52 weeks)
- Follow-up period (4 weeks)
- In addition, the sponsor will offer the possibility to the patients to receive pirfenidone within the study protocol after the Follow-up visit at week 56 for up to 11 months safety follow-up. During this time, the patients should be evaluated by the treating physician approximately every three months.

At the start of Screening, patients will have been on oral pirfenidone taken TID for at least 12 weeks, and the dose will have been in the range of 1602 to 2403 mg/day, for at least 4 weeks prior to the first Screening Visit. It is expected that the dose will remain within the range of 1602 to 2403 mg/day throughout the study and in accordance with the product label. In addition, in the 4 weeks prior to the first Screening Visit, patients must not have experienced either a new or ongoing adverse event of National Cancer Institute Common Terminology Criteria for Adverse Events (NCI CTCAE) version 4.03, which is Grade 2 or higher and considered, by the Investigator to be related to pirfenidone, or have had an interruption of pirfenidone treatment of >7 days for any reason.

During Screening, patients may return for the Baseline visit (Day 1) as soon as eligibility has been confirmed.

Patients who meet all eligibility criteria and who provide written, informed consent will be randomized 1:1 to receive 1 year (52 weeks) of treatment with either oral sildenafil (20 mg) or matching placebo TID while continuing to take pirfenidone. Treatment with sildenafil should be initiated and monitored by a physician experienced in the treatment of PAH.

[figure not shown]
Approximately 176 patients will be enrolled at approximately 75 study centers in Canada, Europe (EU) and Eastern Europe, Middle East, and Africa (EEMEA), *and potentially Asia-Pacific*. No replacements will be made.

Patients who experience a primary endpoint (a decline in 6MWD as defined per protocol or an event of respiratory-related non-elective hospitalization) will continue treatment and be encouraged to complete the study.

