4.3.2.3.2 Sildenafil

Sildenafil may cause decreases in blood pressure due to vasodilator effects. Patients should be treated with caution if they have: resting hypotension (blood pressure [BP] $<90/50$ mmHg), hypertension (BP $>170/110$ mmHg), fluid depletion, severe left ventricular outflow obstruction, or autonomic dysfunction, and also patients receiving

alpha blockers or other antihypertensive medication. Sildenafil is not recommended for use in patients with pulmonary veno-occlusive disease.

In post-marketing experience with sildenafil for male erectile dysfunction, serious cardiovascular events, including myocardial infarction, unstable angina, sudden cardiac death, ventricular arrhythmia, cerebrovascular hemorrhage, transient ischemic attack, hypertension and hypotension have been reported in temporal association with the use of sildenafil. Most, but not all, of these patients had pre-existing cardiovascular risk factors. Sildenafil should be used with caution in patients with cardiovascular disease, in patients receiving concurrent bosentan and in patients with bleeding disorders or with active peptic ulcer disease; as safety and efficacy have not been established.

Sildenafil should be used with caution in patients with anatomical deformation of the penis (angulation, cavernosal fibrosis, or Peyronie's disease), or in patients who have conditions which may predispose them to priapism (sickle cell anemia, multiple myeloma, leukemia). In the event of an erection that persists longer than 4 h, the patient should seek immediate medical assistance. If priapism is not treated immediately, penile tissue damage and permanent loss of potency could result.

Rare cases of NAION have been reported; risk may be increased with history of vision loss. In the event of any sudden visual defect, the treatment should be stopped immediately and alternative treatment should be considered.

Sildenafil may cause dose-related impairment of color discrimination and should be used with caution in patients with retinitis pigmentosa.

Cases of sudden decrease in hearing and hearing loss with the use of PDE5 inhibitors such as sildenafil have been reported.

Orthostatic hypotension has occurred rarely in patients receiving sildenafil (<2%).

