4.3.2.5 Dose Modification or Discontinuation

The Investigator will be responsible for monitoring patients as frequently as clinically indicated for treatment-emergent adverse events or other toxicities, and for doing so in a manner consistent with the instructions in the labels for pirfenidone, sildenafil, and any other medications used to treat a study patient. The Investigator may contact the Medical Monitor or designee to discuss dose modification or discontinuation of study treatment. All treatment-emergent adverse events and toxicities will be followed according to procedures in this protocol. If a patient experiences a clinically significant treatment-emergent adverse event or toxicity, treatment of symptoms and/or temporary dose reduction, interruption, or discontinuation of study treatment should be considered. All changes in dosing will be recorded by the patient in the patient diary and by the study center in the electronic eCRF.

If a patient is hospitalized for any reason, the Investigator should consider continuing the study treatment if appropriate. If the patient is hospitalized at an institution that is not affiliated with the study center, the Investigator is encouraged to discuss study participation with the treating physician at the earliest possible time. All records pertaining to the hospitalization should be obtained by the study center. The Investigator will be responsible for determining the reason for hospitalization (admission to the hospital) (respiratory, cardiac, other), distinguishing elective from non-elective hospitalization, and determining the cause of death (respiratory, cardiac, other). The sections below identify events that require interruption/discontinuation of study treatment, and provide guidance for modifying doses, restarting treatment after an interruption.

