4.5.16 Patient Study Treatment Discontinuation

Patients must discontinue study treatment (sildenafil and/or pirfenidone) if they experience any of the following (see also [Sections 5.1.1](#) and [5.1.2](#)):

- Inability to tolerate study treatment after efforts have been made to gain tolerability
- An elevation in liver test results of the magnitude described below
- Use of a prohibited investigational therapy or concomitant medication
- Sildenafil/placebo will be stopped in patients with acute coronary syndromes, atrioventricular AV block, life-threatening arrhythmias, left ventricular dysfunction (ejection fraction <25%), or clinically significant visual changes
- Pregnancy
- Signs or symptoms of angioedema
- Any other treatment-emergent adverse event or toxicity that is unacceptable in the opinion of the patient or Investigator

Sildenafil/placebo will be stopped (temporarily or permanently) in any patient with systolic blood pressure (SBP) <100 mmHg or diastolic blood pressure (DBP) <50 mmHg.

The primary reason for study treatment discontinuation should be documented on the appropriate eCRF. Patients who discontinue study treatment prematurely will not be replaced.

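### The crude 52-week chi-square without imputation counts patients who leave event-free as non-progressors, and 176 patients leave no room for loss

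*Protocol*

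**What the plan says.** - **Primary analysis (6.4, 6.4.1).** A chi-square test, one-sided 5%, on the proportion progressing over 52 weeks. "The primary and secondary efficacy analyses will include all randomized patients". On missing follow-up: "Patients who discontinue treatment prematurely will be analyzed based on the available data. No imputation method will be applied". Only the details of sensitivity analyses are passed to the SAP.
- **Transplantation (6.4.1).** "Patients who undergo lung transplantation during the study will be withdrawn from the study at the time of hospitalization for transplantation". It is not a component of the composite. Under 4.3.2.5 the investigator classifies the cause of each admission and is responsible for "distinguishing elective from non-elective hospitalization".
- **Leaving the study (4.5.15).** Patients are not followed once consent is withdrawn, and those who withdraw are not replaced.
- **Stopping study drug.** Under 3.1, patients who reach a walk-distance or hospitalization endpoint "will continue treatment and be encouraged to complete the study". Section 4.5.16 has no matching sentence for patients who stop drug, and Appendix 1 gives treatment discontinuation and study withdrawal one shared column.
- **Sample size (6.1).** The calculation "assumes 80% power and a one-sided significance level of 5"%, with 72% v 54%, about 176 patients randomized 1:1, and no dropout rate.

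**The concern.** The protocol does not say outright how an event-free leaver is classified, but its rules leave one answer. Every randomized patient is in the denominator, nothing is imputed, and only observed events enter the numerator. Dropping leavers from the denominator would contradict 6.4. Events recorded before leaving still count, so the problem is confined to event-free leavers. A transplanted patient may join them, unless the admission is classed as respiratory-related and non-elective, which 6.4.1 does not settle.

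Two things are at stake. Equal loss lowers both observed proportions, shrinks their difference and takes power below 80%. Unequal loss makes the arm that loses more patients look better and shifts the error rate of the only confirmatory test.

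Unequal loss is an assumption, but the protocol contains one route to it. Section 4.3.2.3.2 notes that "Sildenafil may cause decreases in blood pressure due to vasodilator effects", and 4.5.16 says that "Sildenafil/placebo will be stopped (temporarily or permanently) in any patient with systolic blood pressure" (or diastolic pressure) below a threshold. Drug stopping may therefore differ by arm, and it turns into loss if assessments end with it.

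**Working it through.** **1. The plan's own figure.** Inputs from 6.1: p1 = 0.72, p2 = 0.54, one-sided α = 0.05, power 0.80. Pooled-variance formula, with p̄ = 0.63:

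n per arm = [1.645·√(2p̄(1−p̄)) + 0.842·√(p1(1−p1) + p2(1−p2))]² / (p1−p2)²
= [1.645·√0.4662 + 0.842·√0.4500]² / 0.0324 = 87.91

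This rounds to 88 per arm, or 176 in total, with power 80.04%. The stated number is reproduced with zero loss.

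**2. Observed crude proportion under dropout.** Assume constant hazards and dropout independent of progression. With le = −ln(1−p) and ld = −ln(1−d), where d is the 52-week dropout probability:

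observed proportion = le/(le+ld) · [1 − (1−p)(1−d)]

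Example, p = 0.72 and d = 0.10: le = 1.273, ld = 0.105, so 0.9235 × (1 − 0.28 × 0.90) = 0.691.

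**3. Equal dropout, 88 per arm.** Power = Φ{[Δ − 1.645·√(2p̄(1−p̄)/88)] / √([p1(1−p1)+p2(1−p2)]/88)}, using the observed proportions.

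| Dropout | Placebo | Sildenafil | Power | N for 80% |
|---|---|---|---|---|
| 0% | 0.720 | 0.540 | 80.0% | 176 |
| 5% | 0.706 | 0.528 | 78.5% | 184 |
| 10% | 0.691 | 0.516 | 77.0% | 192 |
| 20% | 0.660 | 0.491 | 73.8% | 210 |

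**4. Unequal dropout, no true effect (72% in both arms).** Same formulas; one-sided rejection in favour of sildenafil, nominal 5%.

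| Dropout pair | Lower on placebo, higher on sildenafil | Reversed |
|---|---|---|
| 10% and 12% | 5.9% | 4.2% |
| 10% and 15% | 7.6% | 3.1% |
| 10% and 20% | 11.3% | 1.9% |

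**5. Unequal dropout, true 18-point effect.** At 10% (placebo) v 20% (sildenafil) the observed difference is 0.691 − 0.491 = 20.0 points. At 20% v 10% it is 0.660 − 0.516 = 14.4 points, with power 61.9%.

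**6. Kaplan-Meier 52-week proportions instead.** Simulation, 20,000 runs, 88 per arm; walk tests on Days 45, 90, 180, 270 and 365, each moved by up to 5 days; all or half of events (assumed) seen only at walk tests; difference tested with Greenwood standard errors.

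- Error at 10% v 20%, either direction: 4.8% to 5.8%. Smaller 4,000-run simulations gave about 4% to 6.5%.
- Power: 80% to 81% without dropout, 78% at 10%, 75% at 20%.
- Informative loss (assumed shared gamma frailty, variance 0.5 or 1; half of events at visits), 10% v 20%: error 6.3% or 6.5%, against 12.2% or 10.9% for the crude test.
- A trap in implementation: if completers are censored at their actual Week 52 visit day and the curve is read at Day 370, then even without dropout 72% reads as 80% to 84%, error is about 10% and power is 46% to 56%.

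**The case against.** - **The quoted sentence concerns stopping treatment, not leaving the study, and nowhere is a leaver called a non-progressor.** True. The classification is inferred from 6.4 and 6.4.1 together, but the only alternative contradicts 6.4 and also costs power. The SAP was not available; 6.4.1 defers only sensitivity analyses to it, and those would not alter the primary rule.
- **The blood-pressure route is thin.** It needs a lasting drug stop, assessments ending, no earlier event and an imbalance between arms. Patients with low blood pressure are excluded at entry, 4.5.16 allows a temporary stop, and 4.3.2.3.2 puts orthostatic hypotension below 2%, though that is not the stopping threshold. This stands as a limit on size: nothing in the protocol supports a 10-point imbalance, and 10% v 12% (error 5.9%) is closer to its text than 10% v 20%.
- **Section 4.5.15 asks for efforts to keep patients on treatment and to obtain information on those who withdraw.** It does, but it does not require assessments to continue after drug is stopped.
- **The 72% may already contain losses from the source trials.** If so, the power figures overstate the shortfall. This cannot be checked from the protocol, and it does not affect the bias from unequal loss.
- **Kaplan-Meier gains little power and assumes non-informative loss.** Both are correct. Under equal loss the gain is about 1 point or less. The case for it is error control when loss is unequal. Transplant patients would still be censored in the primary test, hence the sensitivity analysis below.

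**Conclusion.** The concern holds and should be fixed. As written, the primary test treats event-free leavers as non-progressors, and the stated 80% power holds only if nobody is lost. Equal dropout of 5% to 20% costs about 1.5 to 6 points of power. Unequal dropout moves the one-sided error to between 1.9% and 11.3% over the range examined, in a direction that cannot be predicted.

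These sizes rest on assumed dropout rates, constant hazards and, except in the frailty simulations, loss unrelated to progression. The sample-size part needs none of these: 176 is the requirement at zero loss.

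**What to change.** 1. **Section 6.4.1.** Compare Kaplan-Meier 52-week progression proportions (difference with Greenwood standard error, one-sided 5%). Censor only patients who leave early, at their last assessment. Either place walk-test events on nominal visit days and read at Day 365, or give patients who complete the Week 52 visit event-free follow-up to Day 370 and read there. Do not censor completers at their actual Week 52 day. State that the analysis assumes non-informative loss. Add a sensitivity analysis, with detail in the SAP if preferred, that counts transplantation and walk tests not done because of the patient's condition as progression.
2. **Section 4.5.16 and Appendix 1.** State that patients who stop study drug remain in the study and keep their assessments to Week 52 unless consent is withdrawn. Separate treatment discontinuation from study withdrawal in the schedule.
3. **Section 6.1.** State that 80% power assumes no loss, and give power over a stated dropout range.

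**Cost.** Wording in four places; Kaplan-Meier is already planned for the same composite in 6.4.2. The form of the primary test changes. The declared power becomes less favourable, about 78% at 10% dropout and 75% at 20%. Bias from informative loss is reduced but remains. Sites carry out already scheduled visits for patients off drug. No extra patients are needed; keeping the crude test at 80% power would take 192 patients at 10% equal dropout or 210 at 20%, and would leave the bias from unequal loss in place.

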1.3 STUDY RATIONALE AND BENEFIT-RISK ASSESSMENT

The diagnosis of IPF carries a bleak prognosis, with progressive disability due to respiratory insufficiency (Hallstrand et al. 2005). Pulmonary hypertension is a major contributor to morbidity and mortality in patients with advanced IPF with an adverse impact on survival (Nadrous et al. 2005, Lettieri et al. 2006.). This study is designed to assess the treatment of patients with advanced IPF who have evidence suggesting PH, that is most likely caused by IPF.

While drugs used to treat PH have either not been effective for treatment of IPF (bosentan, ambrisentan, macitentan) or are unlikely to be able to address the parenchymal changes in the fibrotic process, anti-fibrotic drugs are unlikely to have any

notable effect on the perfusion aspects of interstitial lung diseases (ILDs). Therefore, combination treatment appears as a promising approach to the major clinical problem of combined IPF and PH ([Wuyts et al. 2014](#)).

In this study, pirfenidone (Esbriet[®]) administration will be combined with sildenafil. As sildenafil induces vasodilatation preferentially in well-ventilated lung areas, such vasodilatation could improve ventilation-perfusion matching and thus gas exchange in patients with IPF ([Ghofrani et al. 2002](#)). The combination of pirfenidone and sildenafil represents a promising approach to treat patients with advanced IPF and secondary PH.

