4.1.2 Exclusion Criteria

Patients who meet any of the following criteria will be excluded from study entry:

1. History of any of the following types of PH: Group 1 (PAH); Group 1 (pulmonary veno-occlusive disease and/or pulmonary capillary hemangiomatosis); Group 2 (left-heart disease); Group 3 (due to conditions other than interstitial lung disease, including chronic obstructive pulmonary disease [COPD], sleep-disordered breathing, alveolar hypoventilation, high

altitude, or developmental abnormalities); Group 4 (chronic thromboembolic pulmonary hypertension); Group 5 (other disorders) ([Simonneau et al. 2013](#))

2. History of clinically significant cardiac disease in the opinion of the Investigator, including, but not limited to: left ventricular ejection fraction <40%, congestive heart failure Class IV New York Heart Association (NYHA), left ventricular outflow obstruction (aortic stenosis, idiopathic hypertrophic subaortic stenosis), symptomatic coronary artery disease, congestive heart failure requiring hospitalization, second- or third-degree atrioventricular block, uncontrolled or clinically significant arrhythmias; uncontrolled systemic hypertension
3. History of coexistent and clinically significant (in the opinion of the Investigator) COPD (including chronic bronchitis, emphysema), bronchiectasis, asthma, inadequately treated sleep-disordered breathing, or any clinically significant pulmonary diseases or disorders other than IPF or PH secondary to IPF
4. Hypotension (blood pressure [BP] <100 mmHg systolic or <50 mmHg diastolic), autonomic dysfunction, or conditions in which vasodilation may cause an unsafe drop in blood pressure
5. History of use of drugs and toxins known to cause PAH, including aminorex, fenfluramine, dexenfluramine, and amphetamines. (For a full list see [Galie et al, 2015](#))
6. Initiating any new cardiac or pulmonary rehabilitation program within 28 days prior to Screening and throughout the study
7. FEV1/FVC ratio <0.70 post bronchodilator at Screening
8. Any impairment other than dyspnea that limits the patient's ability to walk for at least 6 minutes or perform other study procedures
9. SpO2 saturation measured by pulse oximetry at rest <92% with ≥6 L of supplemental oxygen, at the first Screening Visit
10. Significant clinical worsening of IPF between the first Screening Visit and Day 1, in the opinion of the Investigator

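### Read literally, the primary endpoint does not count a patient still in the study who is too ill to perform the walk test, unless another qualifying event occurs

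*Protocol*

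**What the plan says.** Protocol Section 6.4.1 defines progression over 52 weeks as a relevant fall in 6MWD, a respiratory-related non-elective hospitalization, or death from any cause. The walk component has two routes. The first is "Any decline >25% from baseline or"; the second is a fall of 15-25% together with worse desaturation, a worse Borg score or a greater oxygen need in the test. Both routes need a recorded distance. The synopsis, Section 2 and Table 1 repeat the definition. Section 6.4.2 refers back to it for progression-free survival and for the proportion with a 6MWD decline.

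Sections 6.4 and 6.4.1 put all randomized patients in the primary analysis. On incomplete data, Section 6.4.1 says: "Patients who discontinue treatment prematurely will be analyzed based on the available data. No imputation method will be applied". It leaves only the details of sensitivity analyses to the SAP.

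Section 4.5.9 asks for one test at each scheduled post-baseline visit and refers to the Procedure Manual for its conduct. It does not say how a test that the patient could not perform is scored.

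On the population, Section 4.1.1 admits patients with DLCO of 40% predicted or less and a 6MWD as low as 100 m. Exclusion 8 in Section 4.1.2 removes "Any impairment other than dyspnea that limits the patient's ability to walk for at least 6 minutes or perform other study procedures", so a patient whose walking is limited by dyspnea may enter. Section 1.3 describes the expected course: "The diagnosis of IPF carries a bleak prognosis, with progressive disability due to respiratory insufficiency".

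**The concern.** The walk component is there to register loss of exercise capacity. Losing the ability to do the test at all, because of breathlessness or hypoxemia, is a more severe loss than a walk shortened by a quarter. Yet it produces no distance, and so no percent fall. With a fixed denominator of all randomized patients, events counted only when evidenced, and no imputation, such a patient falls on the non-event side.

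The missingness is informative: the value is absent because the disease has worsened. Two things are at stake. Some true progressors may be lost from both arms, which shrinks the contrast. And if the loss differs between arms, the contrast is biased in a direction that cannot be known in advance. The same gap carries over to the two secondary endpoints that borrow the definition.

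**Working it through.** **Step 1. Which patients are affected.** To be missed, a patient must meet all four conditions:

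- a scheduled walk is not performed, or is stopped with no distance recorded, for a cardiorespiratory reason;
- no qualifying fall is measured at any other scheduled test (Appendix 1 places post-baseline tests at Weeks 6, 12, 26, 39 and 52);
- no respiratory-related non-elective hospitalization occurs within 52 weeks;
- the patient is alive at Week 52.

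A test that is started and stopped early with a short distance recorded already counts as a fall and is not in question.

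**Step 2. Reproduce the planned size.** The inputs are in Section 6.1: "Given the disease progression rate of 72% by 52 weeks" for pirfenidone, "a disease progression rate of 54% in the combination treatment group is assumed", 1:1 allocation, and a calculation that "assumes 80% power and a one-sided significance level of 5" per cent. For the two-proportion test without continuity correction, with p̄ the mean of the two rates,

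n per arm = [1.645·√(2p̄(1−p̄)) + 0.842·√(p1(1−p1) + p2(1−p2))]² / (p1−p2)²

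with p1 = 0.72, p2 = 0.54, p̄ = 0.63:

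n = [1.645·√0.4662 + 0.842·√0.4500]² / 0.18² = 87.9, rounded up to 88.

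That is 176 in total and matches "A total sample size of approximately 176 patients is planned". Power at 88 per arm is 80.0%. The 176 contains no allowance for missed events.

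**Step 3. Equal loss in both arms (illustration).** Let m be the share of progressors whose only evidence is a walk not performed. The documents give no value for m. Assume also that 72% and 54% include such patients. The observed rates are then 0.72(1−m) and 0.54(1−m), and

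power = Φ{[(p1−p2)·√88 − 1.645·√(2p̄(1−p̄))] / √(p1(1−p1) + p2(1−p2))}.

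| m | Placebo | Sildenafil | Difference | Power | Total N for 80% |
|---|---|---|---|---|---|
| 0 | 72.0% | 54.0% | 18.0 points | 80.0% | 176 |
| 2% | 70.6% | 52.9% | 17.6 points | 78.1% | 186 |
| 5% | 68.4% | 51.3% | 17.1 points | 75.2% | 202 |
| 10% | 64.8% | 48.6% | 16.2 points | 70.2% | 230 |

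In patients, m = 5% is 0.05 × 0.72 × 88 ≈ 3 on placebo and 0.05 × 0.54 × 88 ≈ 2 on sildenafil.

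**Step 4. The same calculation if the base excludes such patients.** Section 6.1 describes the 72% as coming from a 6MWD fall of at least 15%, cardiac or respiratory non-elective hospitalization, or death in pooled earlier trials. It names no category for inability to walk. If those trials also counted measured falls only, 72% is already the rate the current wording would observe, and power against plan stays at 80%.

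**Step 5. Unequal loss (illustration).** From the planned rates, missing 10% of progressors on placebo only gives 64.8% versus 54.0%, a difference of 10.8 points and power of 42.6%. Missing 5% on sildenafil only gives 72.0% versus 51.3%, an inflated difference of 20.7 points. With a true rate of 72% in both arms, missing 5% of progressors on sildenafil only (72.0% versus 68.4%) raises the one-sided rejection rate from 5% to about 13%. These show the direction and sensitivity of the bias; they are not predictions.

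**The case against.** The strongest reply is that the gap may be closed in a document not shown. Section 4.5 says that the manuals give full details of each procedure, and the Procedure Manual might tell sites what to enter for a walk that could not be done. This stands in part: nobody can say from the protocol that the reason is not collected. But Section 6.4.1 itself fixes the event definition, the denominator and the no-imputation rule, and defers only sensitivity analyses. Entering 0 m for an unperformed test would sit uneasily with that rule.

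A second reply is that the no-imputation sentence follows one about patients who stop treatment, so it may concern only them. The sentence carries no such limit and stands in the paragraph that governs the primary analysis. It remains true that the protocol nowhere says in words that such a patient is a non-progressor; this is the literal reading of three rules taken together. Dropping these patients from the denominator would cost little power (about 79% at m of 5% or 10%), but would contradict the all-randomized rule.

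A third reply is that few patients meet all four conditions in Step 1. That stands. Nor does exclusion 8, which applies at entry, show that later inability to walk is mostly due to the disease.

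A reader might also infer that harm like that in the riociguat study would be hidden. The documents do not support this. Section 1.3 describes that signal as deaths and other serious adverse events; all-cause death is part of the composite, and Section 5.1 sends mortality and hospitalizations to the iDMC. A reader might likewise infer that sites will record such tests differently, some as 0 m and some as not done. Without the Procedure Manual, that is conjecture.

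**Conclusion.** The point holds as a defect in the endpoint definition. Followed as written, Section 6.4.1 does not count inability to walk from cardiorespiratory worsening as progression when no other qualifying event occurs, yet counts a milder measured loss.

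Its size is unknown and probably small. The fall in power to about 78%, 75% or 70% rests on two assumptions that the documents neither give nor exclude: a missed share of 2%, 5% or 10%, equal in both arms, and planning rates that include such patients. A reader might conclude from those figures that the trial is underpowered against its own plan. That does not follow: 176 is correct on its stated inputs, and if the 72% rests on measured falls only, planned power is untouched. What survives under either reading is that the misclassification is informative and could bias the comparison if it differs between arms. That justifies a correction at low cost; it does not call the design into question.

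**What to change.** In Section 6.4.1, and where the definition is repeated (synopsis, Section 2, Table 1), add: a scheduled 6MWT not performed, or stopped without a distance, because the patient is unable to walk for a cardiorespiratory reason counts as a relevant decline on that visit date. Make clear that progression-free survival and the 6MWD-decline endpoint in Section 6.4.2 take the same rule by reference. Tests missed for other reasons stay as now.

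Make sure that the eCRF captures the reason for each 6MWT not done (cardiorespiratory, other medical, administrative), completed blinded at the visit, since it may not be recoverable reliably later.

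The rule defines an event from an observed fact, so it does not conflict with the absence of imputation. The cost is one sentence and, if not already there, one data field. The downside is that the reason is an investigator's judgment, and a single missed test can then make an event; blinding limits the scope for bias between arms.
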